- Population and demographic registers
- Registers of catchment of medical care or assurance
- Registers of vaccinations
- Registers of GP/primary health care visits and diagnoses
- Registers of outpatient and inpatient visits and diagnoses in secondary health care
- Registers for reimbursement (medicines, vaccines, medical treatments/measures for outcome or chronic diseases)

- Registers for prescriptions and those showing evidence of pharmacy delivery (medicines, vaccines)
 - Registers for diagnostic microbiological test results
 - Causes of death registers
 - Medical birth registers (timing of pregnancy, perinatal and congenital problems)
 - Cancer registers
 - Registers for congenital malformations
 - Registers of housing, nursing and other social services
 - Registers established for study purposes
- *Each study site to describe the databases (contents, origin) that will be used in the study for assessing information of the exposure, defined outcomes and data of potential confounders and effect modifiers will be derived from (see sections Outcome, Exposure, and Potential confounders and effect modifiers).*

Sample size considerations

This section gives sample size considerations and formulates recommendations. These recommendations are meant to support the design of the cohort studies on IVE. Obtaining a minimum sample size is not a requirement for study participation. Details on the sample size calculations based on the minimal detectable VE as well as precision are given in Annex 3.

DRIVE recommends cohort studies based on 5000 subjects or more. However, studies with smaller sample sizes might still contribute to the power of the pooled analyses, provided that the study site is able to optimally harmonise its protocol with the other study sites to minimize the between-study heterogeneity. In case VE estimates with unacceptable large CIs are obtained, it might be considered to not report these estimates.

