Figure 1 presents the precision of the overall VE for total sample sizes (cohort sizes) varying from 1,000 to 50,000 subjects, when assuming a true VE of 50%, an influenza attack rate in the unvaccinated of 5% and a total vaccination coverage of 5%, 20%, 50% and 70%. The calculations are based on an anticipated true VE of 50% as this is a conservative choice, requiring larger sample sizes compared to assuming lower/higher VE values. A cohort study based on 5000 subjects will result in 95% CIs of the overall VE with a lower limit larger than 25% given a true VE of 50% and an influenza attack rate of 5%, for coverages of >20%.

[figure not shown]
[figure not shown]
[figure not shown]

Figure 1. Precision of the overall VE expressed as the lower limit of the 95% CI, assuming a true VE of 50% (indicated with the black horizontal line), an attack rate in the unvaccinated of 5% and a total vaccination coverage of 5%, 20%, 50% and 70%.

[figure not shown]
Figure 2 presents the precision of the brand-specific VE for total sample sizes (cohort sizes) varying from 1,000 to 50,000 subjects for the same parameter settings as above and additionally assuming the brand of interest accounts for 10%, 20%, 40%, 60%, 80% and 90% of the total vaccination coverage. A cohort study based on 5000 subjects will result in 95% CIs of the brand-specific VE with a lower limit larger than 25% given a true VE of 50% and an influenza attack rate of 5%, for brands covering 40% to 90% of the influenza vaccines when the overall vaccination coverage is 50% or more.

[figure not shown]
a) Total coverage: 5%

b) Total coverage: 20%

c) Total coverage: 50%

d) Total coverage: 70%

Figure 2. Precision of the overall VE expressed as the lower limit of the 95% CI, assuming a true VE of 50% (indicated with the black horizontal line), an attack rate in the unvaccinated of 5%, a total vaccination coverage of 5%, 20%, 50% and 70% and that the brand of interest accounts for 10%, 20%, 40%, 60%, 80% and 90% of the total vaccination coverage.

Data management

Each study site is responsible for the data collection, data validation, and data management of their individual study. DRIVE has developed a generic data management plan (task 4.2.1) and set up the necessary infrastructure for data collection and analysis of the pooled data (task 4.2.2).

- *Each study site to specify how data are collected and validated.*
- *Each study site to specify procedures of data management.*

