The results for the minimal detectable overall VE are given in Figure 1. These figures represent the minimal detectable VE by total sample size. The results for the minimal detectable brand-specific VE for 5% and 15% attack rates in the unvaccinated are given in Figure 2 and Figure 3, respectively.

[figure not shown]

Figure 1. Minimal detectable overall VE for a cohort study assuming vaccination coverage of 5%, 20%, 50% and 70%, and 5% and 15% attack rate in the unvaccinated, by total sample size.

[figure not shown]
[figure not shown]
[figure not shown]

[figure not shown]
Figure 2. Minimal detectable brand-specific VE for a cohort study assuming 5%, 20%, 50% and 70% overall vaccination coverage with the brand of interest covering 10%, 20%, 40%, 60%, 80% and 90% of the overall coverage and 5% attack rate in the unvaccinated, by total sample size.

[figure not shown]
a) 5% overall coverage

b) 20% overall coverage

c) 50% overall coverage

d) 70% overall coverage

Figure 3. Minimal detectable brand-specific VE for a cohort study assuming 5%, 20%, 50% and 70% overall vaccination coverage with the brand of interest covering 10%, 20%, 40%, 60%, 80% and 90% of the overall coverage and 15% attack rate in the unvaccinated, by total sample size.

Precision

The precision refers to the level of sampling error. The standard error and consequently the width of confidence intervals (CI) are measures of precision. As the VE CI are asymmetric, we express precision as the lower limit of the two-sided CI of the anticipated true VE, expressed in %.

For a cohort study, the precision can be derived starting from the anticipated true VE, the confidence coefficient ($1 - \alpha/2$), the total sample size N, the attack rate AR in the unvaccinated and the overall vaccination coverage γ .

Then, from the lower limit of the CI for VE based on cohort studies, or

$$VE_{LL\ CI} = 1 - \exp \left[\log(RR) + Z_{\alpha/2} \sqrt{\frac{1}{A_1} - \frac{1}{N_1} + \frac{1}{A_0} - \frac{1}{N_0}} \right], \quad (3)$$

where $RR = 1 - VE$, $Z_{\alpha/2}$ is the standard normal z-score, A_1 and A_0 are the number of exposed and unexposed cases and where N_1 and N_0 are the number of exposed and unexposed subjects, it follows that the precision is determined for given values A_1 , A_0 , N_1 and N_0 .

The values for A_1 , A_0 , N_1 and N_0 can be derived from the sample size N, the attack rate AR and the overall vaccination coverage γ , or

$$A_1 = N * \gamma * AR * (1 - VE)$$

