[figure not shown]
$$A_0 = N * (1 - \gamma) * AR$$

$$N_1 = N * \gamma$$

[figure not shown]
$$N_0 = N * (1 - \gamma)$$

We calculated precision of the overall VE based on a two-sided 95% CI for cohort studies with the total number of subjects varying from 1000 to 50000, whilst assuming overall vaccination coverages of 5%, 20%, 50% and 70%, VE of 20%, 50% and 70%, and an attack rate in the unvaccinated of 5% and 15%. To calculate the precision of the brand-specific VE, we additionally assumed that the brand of interest accounts for 10%, 20%, 40%, 60%, 80% and 90% of the overall vaccination coverage

[figure not shown]
The results for precision of the overall VE assuming attack rates in the unvaccinated of 5% and 15% are given in Figures 4 and 5, respectively. These figures represent precision by total sample size. The results for the precision of brand-specific VE for anticipated true VE of 20%, 50% and 70%, and 5% attack rate are given in Figures 6 to 8.

a) 20% VE

b) 50% VE

c) 70% VE

Figure 4. Precision of overall VE for a cohort study assuming vaccination coverage of 5%, 20%, 50% and 70%, VE of 20%, 50% and 70% (indicated with the black horizontal line), and 5% attack rate in the unvaccinated, by total sample size.

[figure not shown]
[figure not shown]
[figure not shown]

[figure not shown]
Figure 5. Precision of overall VE for a cohort study assuming vaccination coverage of 5%, 20%, 50% and 70%, VE of 20%, 50% and 70% (indicated with the black horizontal line), and 15% attack rate in the unvaccinated, by total sample size.

[figure not shown]
a) 5% overall coverage

b) 20% overall coverage

[figure not shown]

c) 50% overall coverage

[figure not shown]

d) 70% overall coverage

[figure not shown]
Figure 6. Precision of brand-specific VE for a cohort study assuming an anticipated true VE of 20% (indicated with the black horizontal line), overall vaccination coverage of 5%, 20%, 50% and 70% with the brand of interest covering 10%, 20%, 40%, 60%, 80% and 90% of the overall coverage, and 5% attack rate in the unvaccinated, by total sample size.

[figure not shown]
a) 5% overall coverage

b) 20% overall coverage

[figure not shown]

c) 50% overall coverage

[figure not shown]

d) 70% overall coverage

[figure not shown]

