Figure 7. Precision of brand-specific VE for a cohort study assuming an anticipated true VE of 50% (indicated with the black horizontal line), overall vaccination coverage of 5%, 20%, 50% and 70% with the brand of interest covering 10%, 20%, 40%, 60%, 80% and 90% of the overall coverage, and 5% attack rate in the unvaccinated, by total sample size.

[figure not shown]
a) 5% overall coverage

b) 20% overall coverage

c) 50% overall coverage

d) 70% overall coverage

Figure 8. Precision of brand-specific VE for a cohort study assuming an anticipated true VE of 70% (indicated with the black horizontal line), overall vaccination coverage of 5%, 20%, 50% and 70% with the brand of interest covering 10%, 20%, 40%, 60%, 80% and 90% of the overall coverage, and 5% attack rate in the unvaccinated, by total sample size.

Concluding remarks and recommendations

We make the following observations and recommendations based on our sample size calculations for single-site cohort studies;

- We recommend cohort studies based on 5000 subjects or more. A cohort study with 5000 subjects will result in a minimal detectable overall VE of 30-40% for an influenza attack rate of 5% and coverages >20%.
- A cohort study based on 5000 subjects will result in minimal detectable brand-specific VE of 30-40%, for an influenza attack rate of 5% and brands covering 40% to 90% of the influenza vaccines when the overall vaccination coverage is 50% or more.
- A cohort study with a total sample size of 20.000 will result in a minimal detectable VE of 18-20% for an influenza attack rate of 5% and overall vaccination coverages of 20% or more. Improvements in accuracy both in terms of minimal detectable VE and precision will be minimal when increasing sample sizes further.
- In case higher influenza attack rates (+15%) would be expected, lower sample sizes are needed to obtain VE estimates with acceptable precision.
- In case the VE is expected to be low (< 20%), higher sample sizes are required to obtain VE estimates with acceptable precision.
- In case interest is in VE within subgroups, the sample size calculations should be done with respect to the subgroup-specific sample size.
- **IMPORTANT:** These are recommendations to support the design of cohort studies on (brand-specific) influenza VE. Obtaining a minimum sample size is not a requirement for study participation.

References

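### The main text calls a true VE of 50% conservative against lower as well as higher values; against lower values its own precision formula and Annex 3 show the opposite

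*Combined protocol and SAP*

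**What the plan says.** Under Sample size considerations, the main text advises: "DRIVE recommends cohort studies based on 5000 subjects or more". It supports this with precision curves for overall and brand-specific VE at a true VE of 50%, a 5% attack rate in the unvaccinated and coverage of 5%, 20%, 50% and 70%. It justifies the VE input as "an anticipated true VE of 50% as this is a conservative choice, requiring larger sample sizes compared to assuming lower/higher VE values". It then says that 5000 subjects give a lower 95% limit for overall VE above 25% when coverage exceeds 20%, given VE 50% and a 5% attack rate.

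Annex 3, Precision, sets the scale: "we express precision as the lower limit of the two-sided CI of the anticipated true VE, expressed in" per cent. It gives formula (3) and applies it at VE 20%, 50% and 70% and at attack rates of 5% and 15%. The annex's concluding remarks state: "In case the VE is expected to be low (< 20%), higher sample sizes are required to obtain VE estimates with acceptable precision".

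**The concern.** The main-text clause says that the required sample size is larger at VE 50% than on either side of it. The annex remark says that a low VE needs more subjects. For VE below 20% both cannot be true.

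The clause also tells a site that a low-VE season is the easier case to plan for. The Background acknowledges that VE varies from year to year, with strain mismatch among the reasons, so low VE is foreseeable. This is a generic protocol meant for local adaptation, so the sentence may be carried into site protocols. The main text also allows estimates with very wide intervals to go unreported, so a site that misjudges its precision could lose an estimate.

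**Working it through.** **Inputs.** All come from the protocol's sample size section and Annex 3: N = 5000; attack rate AR = 5% (15% as a variant); coverage g = 5%, 20%, 50%, 70%; VE = 20%, 50%, 70%; two-sided 95% interval, z = 1.96.

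**Formula (3).** LL = 1 − exp[log(1 − VE) + z × SE], with SE² = 1/A1 − 1/N1 + 1/A0 − 1/N0, where A1 = N·g·AR·(1 − VE), A0 = N·(1 − g)·AR, N1 = N·g and N0 = N·(1 − g).

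**Step 1: reproduce the plan's figure (VE 50%, AR 5%).** At g = 20%, A1 = 25, A0 = 200, N1 = 1000 and N0 = 4000. SE² = 0.04 − 0.001 + 0.005 − 0.00025 = 0.04375, SE = 0.2092, and LL = 1 − 0.5 × exp(0.410) = 24.7%. At coverage 21% it is 25.3%, at 50% 32.6% and at 70% 32.3%. The stated limit above 25% for coverage above 20% holds.

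**Step 2: change only VE.** At g = 20% and VE 20%, A1 = 40. SE² = 0.025 − 0.001 + 0.005 − 0.00025 = 0.02875, SE = 0.1696, and LL = 1 − 0.8 × exp(0.332) = −11.5%. The same calculation for the other cells gives the lower limit, with the distance from VE in points in brackets:

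| Coverage | VE 20% | VE 50% | VE 70% |
|---|---|---|---|
| 20% | −11.5% (31.5) | 24.7% (25.3) | 49.5% (20.5) |
| 50% | −3.4% (23.4) | 32.6% (17.4) | 57.0% (13.0) |
| 70% | −5.2% (25.2) | 32.3% (17.7) | 57.5% (12.5) |

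At 5% coverage and VE 20% the lower limit is −48.7%. The distance equals (1 − VE) × (exp(z·SE) − 1). As VE falls, SE shrinks because there are more vaccinated cases, but in these settings 1 − VE grows by more than that saves.

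**Step 3: turn this into sample size.** For a fixed distance d, N = [z × s / ln((1 − VE + d)/(1 − VE))]², where s = SE × √N does not depend on N. Take d = 25 points, which at VE 50% is the plan's own 25% limit. The log term is ln(1.05/0.80) = 0.272 at VE 20% and ln(0.75/0.50) = 0.405 at VE 50%.

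| Coverage | N at VE 20% | N at VE 50% | Increase |
|---|---|---|---|
| 20% | 7,468 | 5,112 | 46% |
| 50% | 4,468 | 2,711 | 65% |
| 70% | 5,071 | 2,782 | 82% |

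A 25-point distance at VE 20% still leaves the limit at −5%. To bring it to zero at VE 20% and AR 5% takes about 11,090, 6,635 and 7,531 subjects at coverage 20%, 50% and 70%.

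**Step 4: vary the attack rate.** At AR 15%, VE 20% and N = 5000, the lower limits are −12.7%, +3.9%, +7.9% and +7.0% at coverage 5%, 20%, 50% and 70%. The ordering by VE is unchanged: at 20% coverage the distances are 16.1, 12.9 and 10.3 points for VE 20%, 50% and 70%.

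**Step 5: try other criteria.** The N for a fixed total interval width and the N for 80% power also fall as VE rises. At AR 5% and 50% coverage, 80% power needs 13,490 subjects at VE 20%, 1,812 at 50% and 804 at 70%. On the standard error of log RR the order reverses, so higher VE needs more subjects. With very few vaccinated cases (5% coverage, N = 1000), the distance is not monotone and very high VE is worst. VE 50% is the most demanding value under none of these.

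**The case against.** The strongest reply concerns consequence. A reader might infer that the plan presents 5000 subjects as covering the worst case. It does not say so: the word conservative describes the VE input, and both 5000-subject precision statements name VE 50% and a 5% attack rate as conditions. A reader might also infer that the 25% statement is wrong, but the overall-VE one reproduces.

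Annex 3 discloses the low-VE limitation. It plots VE 20% (Figures 4a, 5 and 6), and the main text sends readers there. It sets the 5000-subject recommendation beside a minimal detectable overall VE of 30–40%; formula (2) gives 36.6%, 31.8% and 35.7% at coverage 20%, 50% and 70%. It names 20,000 subjects for a minimal detectable VE of 18–20%. The size is advisory, smaller sites may take part, and the data are to be pooled. The clause is also right against higher VE at the recommended size and coverages on the plan's own scale.

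All of this stands, and it limits the harm. It does not make the clause true for lower VE, and figures in an annex do not correct a main-text sentence that says the reverse.

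**Conclusion.** The claim that 50% is conservative relative to lower VE is wrong under the plan's own formula and at odds with Annex 3's concluding remarks. At 5000 subjects and a 5% attack rate, the VE-to-limit distance at VE 20% is about 6 to 7.5 points larger than at VE 50% for coverage of 20% or more. Equal distance needs 46% to 82% more subjects. These figures rest on formula (3), z = 1.96 and the 25-point yardstick.

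A reader might conclude that 5000 subjects cannot exclude zero at VE 20% whatever the setting. That is too broad: it holds at all four coverages at a 5% attack rate, but at 15% the limit is above zero for coverage of 20% or more. The correction should be made, but it alters no design feature, estimand or analysis.

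**What to change.** - In Sample size considerations, delete the claim that 50% is conservative against lower VE. Describe it as a mid-range assumption and say that precision worsens as VE falls.
- Align that text with the Annex 3 remark on low VE.
- Beside the 5000-subject recommendation, cite or show the VE 20% results already produced for Annex 3 (Figures 4a and 6), with the attack rate stated.

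The cost is a text edit with no new data or analysis. The downside is that the stated precision looks less favourable: for example, at VE 20%, 50% coverage and a 5% attack rate, the reader would see a lower limit of −3.4% next to the 32.6% for VE 50%.

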The exposure of interest is vaccination with any seasonal influenza vaccine in the season under investigation (index season). For vaccination status ascertainment, it is crucial to know about the date of vaccine administration and the type/brand of the vaccine. .

The sources of information for the vaccination status may include:

- vaccination registry
- health care visit/hospitalisation register with relevant information of the vaccinations
- relevant insurance company register or prescription register showing evidence of pharmacy delivery or reimbursement of influenza vaccine

- *Each study site to describe the precise way of vaccination status ascertainment.*

Definition of vaccination status

An individual aged ≥ 9 years, or a child aged <9 who has been fully vaccinated before the current season (at least two injectable doses or one LAIV dose) will be considered as

- **vaccinated** with the influenza vaccine of interest (defined exposure) if >14 days have elapsed since the first record of influenza vaccination during the season (see section *Vaccination status ascertainment*)
- **partially vaccinated** during the first 14 days after the first record of vaccination (defined exposure) during the season
- **unvaccinated** until the first vaccination record during the season

A child aged <9 years who has not been fully vaccinated (see above) before the current season will be considered as

- **vaccinated** with the influenza vaccine of interest if >14 days have elapsed since the second record of injectable vaccination or the first record of LAIV vaccination during the current season (see section *Vaccination status ascertainment*)
- **partially vaccinated**
 - during the first 14 days after the second record of injectable vaccination or the first record of LAIV vaccination during the current season
 - after the first record of injectable vaccination until >14 days have elapsed since the second record of vaccination during the current season
- **unvaccinated** until the first vaccination record during the season

If vaccination cannot be assessed as a time-dependent event, and for the description of demographics and baseline characteristics, the vaccination status (yes/no) will be assessed at the end of the individual follow-up.

If the individual has a record of vaccination with a type or brand other than the one of interest (defined exposure) during the study period, she/he will be right-censored at this time point (see section Individual follow-up).

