Annex 3: Sample size considerations for cohort studies

Authors: [name] and [name]

For questions or feedback, please contact

e-mail: [contact]

This document provides sample size estimations for estimating overall and brand-specific influenza vaccine effectiveness (VE) using the cohort design. The minimal detectable VE as well as precision estimates are provided for various parameter settings and recommendations are formulated.

Minimal detectable vaccine effectiveness

The minimal detectable VE is the smallest VE that can be detected as significantly greater than zero in a given study using hypothesis testing. The minimal detectable VE for a cohort study is estimated as

$$VE_{MD} = 1 - RR_{MD(RR<1)}, \quad (1)$$

where $RR_{MD(RR<1)}$ is the minimal detectable relative risk (RR) if $RR < 1$, or

$$RR_{MD(RR<1)} \cong \frac{1}{2a} \left(b - \sqrt{b^2 - 4ac} \right), \quad (2)$$

where

$$a = Y + \pi Z; \quad b = 2Y + Z; \quad c = Y - r(1 - \pi)Z,$$

in which

$$Y = rN\pi^2; \quad Z = (r + 1)\pi \left(z_{\frac{\alpha}{2}} + z_{\beta} \right)^2$$

for attack rate in the unexposed π , exposed to unexposed ratio r with $r = \gamma/(1 - \gamma)$ with coverage γ , total sample size N , and where z_{α} and z_{β} are the standard normal z-score for the type I and type II error rates (Woodward 2013).

We calculated the minimal detectable overall VE (1) with 80% power ($1 - \beta$) and a two-sided 95% confidence coefficient ($1 - \alpha/2$) for cohort studies with the total number of subjects varying from 1000 to 50000, while assuming overall vaccination coverages of 5%, 20%, 50% and 70% and an attack rate of 5% and 15% in the unvaccinated.

We additionally calculated the minimal detectable brand-specific VE, where subjects are considered exposed when they were vaccinated with the brand of interest and unexposed when they were unvaccinated during the study's follow-up. This means that the same comparator group of unexposed subjects is used for the different brand-specific estimates. The minimal detectable brand-specific VE is calculated for the same settings above, additionally assuming that the brand of interest accounts for 10%, 20%, 40%, 60%, 80% and 90% of the overall vaccination coverage.

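### The precision and minimal detectable VE stated for 5000 subjects assume full-season exposure of every vaccinee; under the plan's time-dependent exposure rule they are best-case figures and not assured, mainly at 20-30% coverage and for brands near a 40% share

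*Combined protocol and SAP*

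**What the plan says.** The section on sample size considerations gives the recommendation, "DRIVE recommends cohort studies based on 5000 subjects or more", and supports it by saying that such a cohort "will result in 95% CIs of the overall VE with a lower limit larger than 25% given a true VE of 50" per cent, for a 5% attack rate and coverage above 20%. It makes a similar statement for brands holding 40% to 90% of the vaccine used when overall coverage is at least 50%. The concluding remarks of Annex 3 add that 5000 subjects "will result in a minimal detectable overall VE of 30-40% for an influenza attack rate of 5% and coverages >20" per cent. The power behind that figure is given under minimal detectable vaccine effectiveness: "We calculated the minimal detectable overall VE (1) with 80% power".

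In the precision part of Annex 3, the exposed group is N1 = N × coverage and the exposed cases are A1 = N × coverage × AR × (1 − VE). For the brand calculations, "subjects are considered exposed when they were vaccinated with the brand of interest". No term covers when the dose was given or whether a second dose followed.

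The protocol's definition of vaccination status is narrower. Subjects aged 9 or over, and younger children already fully vaccinated in earlier seasons, count as vaccinated more than 14 days after the first dose. Other children under 9 count "if >14 days have elapsed since the second record of injectable vaccination or the first record of LAIV vaccination during the current season". The section on individual follow-up then splits each subject's person-time into unvaccinated, partially vaccinated and vaccinated time.

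**The concern.** The sample size formulas and the time-dependent analysis do not count the same exposure. A vaccinee's cases before the dose, within 14 days of it, or (for a two-dose child) before day 15 after the second injectable dose are planned as vaccinated cases but will not be analysed as such. A1 is usually the smaller case count at modest coverage and dominates the standard error, so the planned precision is optimistic there.

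The figures are the stated support for the 5000-subject recommendation. They are worded as what a cohort will achieve, with no condition on vaccination timing. This is a generic protocol that sites are meant to adapt. A site with coverage in the twenties, or with a campaign that overlaps the epidemic, could plan on precision that its own exposure rule does not give. Brand-specific VE comes first in the primary objective and has the thinner exposed groups.

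**Working it through.** **Inputs.** N = 5000, AR = 5% in the unvaccinated and VE = 50% come from the sample size section. The 95% two-sided CI (z = 1.96) and 80% power (z = 0.842) come from Annex 3. f is not in the documents and is assumed.

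**1. Reproducing the plan.** Annex 3 formula (3) is: lower limit = 1 − (1 − VE) × exp(1.96 × SE), with SE = √(1/A1 − 1/N1 + 1/A0 − 1/N0).

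At 21% coverage: N1 = 1050, A1 = 26.25, N0 = 3950, A0 = 197.5. SE = 0.2048, and the limit is 1 − 0.5 × exp(0.4015) = 25.3%.

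The limit is 24.7% at 20% coverage, 32.6% at 50% and 32.3% at 70%. It crosses 25% at 20.5% coverage. Formula (2) gives a minimal detectable VE of 36.6%, 31.8% and 35.7% at 20%, 50% and 70%. Both overall statements reproduce to rounding.

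**2. One discount for f.** Set N1 = N × coverage × (1 − f) and A1 = N1 × AR × (1 − VE). As a first pass, drop all the lost time and leave N0 and A0 unchanged.

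At 21% coverage and f = 10%: N1 = 945, A1 = 23.625, SE = 0.2147, and the limit is 23.8%.

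| Coverage | f = 0 | 10% | 20% | 30% | f at which the limit reaches 25% |
|---|---|---|---|---|---|
| 21% | 25.3 | 23.8 | 22.1 | 19.9 | 2.2% |
| 25% | 27.4 | 26.1 | 24.6 | 22.6 | 17% |
| 30% | 29.2 | 28.1 | 26.8 | 25.1 | 30% |
| 50% | 32.6 | 31.9 | 31.0 | 29.8 | 56% |
| 70% | 32.3 | 31.8 | 31.2 | 30.4 | 63% |

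At f = 55% the limit is still 25.2% at 50% coverage and 26.9% at 70%.

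**3. Crediting pre-vaccination time to the unvaccinated.** If all the lost time precedes the dose and joins N0, the limits at 21% coverage for f = 10/20/30% are 23.9/22.2/20.0%, almost unchanged. At 70% coverage, where the comparator is small, the credit offsets the loss: 32.8/32.9/32.5%.

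**4. Minimal detectable overall VE.** Use formula (2) with r = N1/N0 and total N1 + N0. At 21% coverage it goes from 36.1% at f = 0 to 40.2% at f = 30% (39.9% if all the lost time is credited to the unvaccinated). At 25% coverage and f = 30% it is 38.3%. At f = 50% it is 36.9% for 50% coverage and 39.0% for 70%.

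**5. Brand with a 40% share.** At 70% coverage: N1 = 1400, A1 = 35, N0 = 1500, A0 = 75, SE = 0.2013, limit 25.8%. With f = 10%: N1 = 1260, A1 = 31.5, SE = 0.2089, limit 24.7%. If half of the lost time (across all brands' vaccinees) is credited to the unvaccinated, the limit is 25.2% at f = 10% and 24.2% at f = 20%.

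At 50% coverage: N1 = 1000, A1 = 25, N0 = 2500, A0 = 125, SE = 0.2159, limit 23.7% with f = 0. The brand statement therefore already fails at its own boundary, whatever the exposure rule.

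**6. Children under 9 who need two injectable doses.** Suppose every vaccinee needs two doses, 60% complete (an assumption) and nothing else is lost, so f = 40%. The limit is then 17.0/22.9/28.4/29.3% at coverage 21/30/50/70%.

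**The case against.** A reader might infer that the stated precision will not be achieved. The documents do not support that. They give neither the timing of vaccination relative to the epidemic nor second-dose completion, and f is weighted by risk, not by calendar time. If single-dose subjects are vaccinated more than 14 days before circulation starts, their f is zero.

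The failures also lie at coverages between those Annex 3 worked out (5, 20, 50 and 70%). At 21% the margin is only 0.3 points before any discount, so almost any change removes it. At 50% and 70% the overall figures are robust, and at 70% the time returned to the comparator can even raise the limit slightly. These points stand and limit the finding. They do not remove it, because the claim is made for all coverages above 20%.

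Where vaccination cannot be time-dependent, status is yes/no at the end of follow-up and logistic regression is used. Annex 3 fits that case, so those sites are outside this point.

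A reader might also infer that the figures are wrong for children under 9 in general. That goes too far. One LAIV dose, or full vaccination in earlier seasons, leaves a single qualifying dose, and Annex 3 asks for separate subgroup calculations. That advice changes N, however, and not the exposure term. Since databases may be restricted by age, a paediatric cohort can be a site's whole study.

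Finally, the figures are recommendations and no minimum size is required for participation. That limits the consequence, but a stated precision should still match the analysis it describes.

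**Conclusion.** The point holds as an unstated assumption, not as an arithmetic error: the overall figures reproduce from the plan's own formulas. For sites with time-dependent vaccination status they are best-case values, apart from the small offset at 70% coverage noted above.

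The precision claim has almost no margin just above 20% coverage. It fails at an assumed f of about 2% at 21% coverage, 17% at 25% and 30% at 30%. It is secure at 50 to 70% coverage up to f = 55%. Minimal detectable overall VE is barely touched: within f = 0 to 30% it passes 40% only near 21% coverage, at f = 30%. A brand with a 40% share at 70% coverage falls below 25% somewhere between f = 10% and f = 20%, or by f = 10% if no time is credited to the comparator.

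The 23.7% for a 40% share at 50% coverage is a separate error in the brand claim and should not be put down to exposure timing. All sizes rest on the assumed range of f.

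**What to change.** In the sample size section and Annex 3:

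- Keep coverage as the share ever vaccinated, and state that the present figures assume every vaccinee is in the vaccinated state throughout the epidemic.
- Apply the discount once: N1 = N × coverage × (1 − f) and A1 = N1 × AR × (1 − VE). Leave partially vaccinated time out and add pre-vaccination time to the unvaccinated. Coverage must not also be redefined as vaccinated risk time, since that would discount twice.
- Tabulate f from 0 to 30%, with a higher range for cohorts of children under 9 who need two injectable doses.
- Restate the overall claim, for example: lower limit above 25% at coverage from 30% up to the 70% worked out in Annex 3, if at most 30% of vaccinees' risk lies outside the vaccinated state.
- Qualify the brand claim in the same way, and correct its boundary at a 40% share and 50% coverage.
- Note that sites using yes/no status at the end of follow-up take f = 0.

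The cost is a re-run of existing formulas and edits to a few short paragraphs. The stated figures become slightly less favourable. No extra subjects or data are needed.
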